## 9.2 Adverse Events: Lists and Reporting Requirements

Patients will be evaluated for toxicity if they have received at least one dose of TRC102 or temozolomide.

Adverse event (AE) monitoring and reporting is a routine part of every clinical trial. The following list of AEs (Section 9.2.1, below) and the characteristics of an observed AE (Section [9.2.2](#)) will determine whether the event requires expedited reporting via the CTEP Adverse Event Reporting System (CTEP-AERS) **in addition** to routine reporting.

Adverse Events will be collected for at least 30 days following the last dose of study drug.

All adverse events must be reported to the ABTC Central Office and the NCI in the manner described and per the requirements of the investigative site's Institutional Review Board.

Adverse events will be entered into CTEP's Medidata Rave database by the investigative site in a timely manner. See Section [12.0](#) – Records to be Kept.

### 9.2.1 Comprehensive Adverse Events and Potential Risks Lists (CAEPR)

#### 9.2.1.1 Comprehensive Adverse Events and Potential Risks list (CAEPR) for Methoxyamine hydrochloride (TRC102, NSC 3801)

The Comprehensive Adverse Events and Potential Risks list (CAEPR) provides a single list of reported and/or potential adverse events (AE) associated with an agent using a uniform presentation of events by body system. In addition to the comprehensive list, a subset, the Specific Protocol Exceptions to Expedited Reporting (SPEER), appears in a separate column and is identified with bold and italicized text. This subset of AEs (SPEER) is a list of events that are protocol specific exceptions to expedited reporting to NCI (except as noted below). Refer to the 'CTEP, NCI Guidelines: Adverse Event Reporting Requirements'

[http://ctep.cancer.gov/protocolDevelopment/electronic\\_applications/docs/aeguidelines.pdf](http://ctep.cancer.gov/protocolDevelopment/electronic_applications/docs/aeguidelines.pdf) for further clarification. The CAEPR does not provide frequency data; refer to the Investigator's Brochure for this information. Below is the CAEPR for Methoxyamine hydrochloride (TRC102).

**NOTE:** Report AEs on the SPEER **ONLY IF** they exceed the grade noted in parentheses next to the AE in the SPEER. If this CAEPR is part of a combination protocol using multiple investigational agents and has an AE listed on different SPEERs, use the lower of the grades to determine if expedited reporting is required.

Version 1.0, February 8, 2013

Adverse Events with Possible Relationship to Methoxyamine hydrochloride (TRC102) (CTCAE 4.0 Term)		Specific Protocol Exceptions to Expedited Reporting (SPEER)
BLOOD AND LYMPHATIC SYSTEM DISORDERS		
	Anemia	Anemia (Gr 2)
GASTROINTESTINAL DISORDERS		
	Diarrhea	Diarrhea (Gr 1)
	Mucositis oral	Mucositis oral (Gr 1)
	Nausea	Nausea (Gr 2)
	Vomiting	Vomiting (Gr 2)
GENERAL DISORDERS AND ADMINISTRATION SITE CONDITIONS		
	Fatigue	Fatigue (Gr 2)
	Fever	Fever (Gr 1)
INVESTIGATIONS		
	Blood bilirubin increased	Blood bilirubin increased Gr 1
	Haptoglobin decreased	Haptoglobin decreased (Gr 1)
METABOLISM AND NUTRITION DISORDERS		
	Anorexia	Anorexia (Gr 1)
SKIN AND SUBCUTANEOUS TISSUE DISORDERS		
	Pruritus	Pruritus (Gr 1)
	Rash maculo-papular	Rash maculo-papular (Gr 1)

This table will be updated as the toxicity profile of the agent is revised. Updates will be distributed to all Principal Investigators at the time of revision. The current version can be obtained by contacting [[contact]](mailto:[contact]). Your name, the name of the investigator, the protocol and the agent should be included in the e-mail.

**Also reported on methoxyamine hydrochloride (TRC102) trials but with the relationship to methoxyamine hydrochloride (TRC102) still undetermined:**

**BLOOD AND LYMPHATIC SYSTEM DISORDERS** - Hemolysis

**GASTROINTESTINAL DISORDERS** - Constipation

**IMMUNE SYSTEM DISORDERS** – Allergic reaction

**INVESTIGATIONS** - Alanine aminotransferase increased; Aspartate aminotransferase increased; Creatinine increased; Lymphocyte count decreased; Neutrophil count decreased; Platelet count decreased; White blood cell decreased

**METABOLISM AND NUTRITION DISORDERS** - Hypocalcemia

**NERVOUS SYSTEM DISORDERS** - Dysgeusia

**PSYCHIATRIC DISORDERS** – Psychosis

**RESPIRATORY, THORACIC, & MEDIASTINAL DISORDERS** - Dyspnea

**VASCULAR DISORDERS** - Thromboembolic event

**Animal Data: The following toxicities have been observed in animal studies with methoxyamine hydrochloride (TRC102):**

**Dogs:**

**BLOOD AND LYMPHATIC SYSTEM DISORDERS** - bone marrow hypercellularity; epididymal cellular debris; small thymus

**GASTROINTESTINAL DISORDERS** - abnormal excreta

**INVESTIGATIONS** – increased reticulocytes, lymphocytes increased

**NERVOUS SYSTEM DISORDERS** - convulsions; tremors

**REPRODUCTIVE SYSTEM AND BREAST DISORDERS** - seminiferous tubule degeneration

**Rats:**

**BLOOD AND LYMPHATIC SYSTEM DISORDERS** - enlarged or swollen spleens; increased spleen weight

**INVESTIGATIONS** - increased monocytes; increased reticulocytes; lymphocytes increased

**Note:** Methoxyamine hydrochloride (TRC102) in combination with other agents could cause an exacerbation of any adverse event currently known to be caused by the other agent, or the combination may result in events never previously associated with either agent.

### 9.2.1.2 Adverse Event List for Temozolomide

Known potential toxicities of temozolomide are hematological toxicities (leucopenia, lymphopenia, thrombocytopenia, and anemia), renal insufficiency, nausea and vomiting, liver enzyme abnormalities, lethargy, rash, headache, alopecia, constipation, fatigue/malaise, anorexia, hyperglycemia and diarrhea are known toxicities. Recently, cases of hepatic injury, including fatal hepatic failure, have been observed in patients enrolled in clinical studies utilizing the agent temozolomide. In addition, it was noted that liver toxicity may occur several weeks or more after initiation of treatment or after temozolomide discontinuation. Refer to the package insert for additional information on adverse events observed to date.

Rats given temozolomide in recent multidose toxicity studies have developed adenocarcinoma of the breast, fibrosarcomas, malignant Schwannomas (a variant of fibrosarcoma), keratoacanthomas and basal cell adenomas. Similar studies conducted in dogs did not reveal any similar findings. The significance of this finding for humans is not known presently.

Temozolomide is potentially mutagenic and should be handled with appropriate precautions by both staff and subjects. Subjects with known or suspected hypersensitivity to temozolomide should not be treated with temozolomide. There are no data available on the effect or management of temozolomide overdose.

Additional information is available in the temozolomide package insert ([www.temodar.com](http://www.temodar.com)).

### 9.2.2 Adverse Event Characteristics

#### Definition - Adverse Event (AE)

Adverse event is defined as any unfavorable and unintended sign (including an abnormal laboratory finding), symptom or disease temporally associated with the use of a medical treatment or procedure regardless of whether it is considered related to the medical treatment or procedure (attribution of unrelated, unlikely, possible, probable, or definite).

#### Recording of Adverse Events - ABTC AE Form

- The investigator will monitor each patient closely for the development of adverse events and record all such events on the ABTC AE Case Report Form. Each single sign or symptom must be reported separately.
- **CTCAE term (AE description) and grade:** The descriptions and grading scales found in the revised NCI Common Terminology Criteria for Adverse Events (CTCAE) version 4.0 will be utilized for AE reporting. All appropriate treatment areas should have access to a copy of the CTCAE version 4.0. A copy of the CTCAE version 4.0 can be downloaded from the CTEP web site ([http://ctep.cancer.gov/protocolDevelopment/electronic\\_applications/ctc.htm](http://ctep.cancer.gov/protocolDevelopment/electronic_applications/ctc.htm)). You must use one of the CTCAE criteria to define your event.

Adverse events not included in the CTCAE should be reported under “Other” within the appropriate category and graded 1 to 5 according to the general grade definitions - mild, moderate, severe, life-threatening, fatal or disabling - as provided in the CTCAE or the CTCAE Manual. New adverse events may be submitted to the CTEP Help Desk at [[contact]](mailto:[contact]) for annual evaluation by the CTCAE Change Management Committee.

- **For expedited reporting purposes only:** AEs for TRC102 that are ***bold and italicized*** in the CAEPR (*i.e.*, those listed in the SPEER column, Section [9.2.1.1](#)) should be reported through CTEP-AERS only if the grade is above the grade provided in the SPEER.
- **Attribution of the AE:** The investigator will be asked to document his/her opinion of the relationship of the event to study medication as follows:
  - *Unrelated* – The AE is clearly not related to the investigational agent(s).
  - *Unlikely* – The AE is doubtfully related to the investigational agent(s).
  - *Possible* – The AE may be related to the investigational agent(s).
  - *Probable* – The AE is most likely related to the investigational agent(s).
  - *Definite* – The AE is clearly related to the investigational agent(s).
- All adverse events should be followed up in accordance with good medical practice. Abnormalities of laboratory events which, in the opinion of the investigator, constitute adverse events (even if not serious) should be followed.

## 9.3 Serious Adverse Events and Expedited Adverse Event Reporting

### 9.3.1 Definition – Serious Adverse Event (SAE)

An adverse event is considered serious if it results in **ANY** of the following outcomes:

- 1) Death
- 2) A life-threatening adverse event
- 3) An adverse event that results in inpatient hospitalization or prolongation of existing hospitalization for  $\geq 24$  hours

- 4) A persistent or significant incapacity or substantial disruption of the ability to conduct normal life functions
- 5) A congenital anomaly/birth defect
- 6) Important Medical Events (IME) that may not result in death, be life threatening, or require hospitalization may be considered serious when, based upon medical judgment, they may jeopardize the patient or subject and may require medical or surgical intervention to prevent one of the outcomes listed in this definition.

### **9.3.2 Expedited Adverse Event Reporting**

➤ **Use CTEP-AERS Web Application and Document on ABTC AE Form**

- All SAEs must be documented on both the ABTC AE form and using the CTEP-AERS Web Application within 24 hours of learning of the event.
- Expedited AE reporting for this study must use CTEP-AERS (CTEP Adverse Event Reporting System), accessed via the CTEP web site (<https://eapps-ctep.nci.nih.gov/ctepaers>). The reporting procedures to be followed are presented in the “NCI Guidelines for Investigators: Adverse Event Reporting Requirements” which can be downloaded from the CTEP web site ([http://ctep.cancer.gov/protocolDevelopment/electronic\\_applications/adverse\\_events.htm](http://ctep.cancer.gov/protocolDevelopment/electronic_applications/adverse_events.htm)).

In the rare occurrence when Internet connectivity is lost, a 24-hour notification is to be made to CTEP by telephone at [contact]. Once Internet connectivity is restored, the 24-hour notification phoned in must be entered electronically into CTEP-AERS by the original submitter at the site.

- CTEP-AERS is programmed for automatic electronic distribution of reports to the following individuals: Principal Investigator and Adverse Event Coordinator(s) of the Adult Brain Tumor Consortium (ABTC), the local treating physician, and the Reporter and Submitter. CTEP-AERS provides a copy feature for other e-mail recipients.
- The ABTC Central Office is responsible for submitting to the CTSU documentation of AEs that they deem reportable for posting on the CTSU protocol web page and inclusion on the CTSU bi-monthly broadcast.
- Expedited Reporting Guidelines

Use the NCI protocol number and the protocol-specific patient ID provided during trial registration on all reports.

**Note: A death on study requires both routine and expedited reporting regardless of causality, unless as noted below. Attribution to treatment or other cause must be provided.**

Death due to progressive disease should be reported as **Grade 5 “Neoplasms benign, malignant and unspecified (including cysts and polyps) - Other (Progressive Disease)”** under the system organ class (SOC) of the same name. Evidence that the death was a manifestation of underlying disease (e.g., radiological changes suggesting tumor growth or progression; clinical deterioration associated with a disease process) should be submitted.

**Phase 1 and Early Phase 2 Studies: Expedited Reporting Requirements for Adverse Events that Occur on Studies under an IND/IDE within 30 Days of the Last Administration of the Investigational Agent/Intervention**

**FDA REPORTING REQUIREMENTS FOR SERIOUS ADVERSE EVENTS (21 CFR Part 312)**

**NOTE:** Investigators **MUST** immediately report to the sponsor (NCI) **ANY** Serious Adverse Events, whether or not they are considered related to the investigational agent(s)/intervention (21 CFR 312.64)

An adverse event is considered serious if it results in **ANY** of the following outcomes:

- 1) Death
- 2) A life-threatening adverse event
- 3) An adverse event that results in inpatient hospitalization or prolongation of existing hospitalization for  $\geq 24$  hours
- 4) A persistent or significant incapacity or substantial disruption of the ability to conduct normal life functions
- 5) A congenital anomaly/birth defect.
- 6) Important Medical Events (IME) that may not result in death, be life threatening, or require hospitalization may be considered serious when, based upon medical judgment, they may jeopardize the patient or subject and may require medical or surgical intervention to prevent one of the outcomes listed in this definition. (FDA, 21 CFR 312.32; ICH E2A and ICH E6).

**ALL SERIOUS** adverse events that meet the above criteria **MUST** be immediately reported to the NCI via electronic submission within the timeframes detailed in the table below.

Hospitalization	Grade 1 and Grade 2 Timeframes	Grade 3-5 Timeframes
Resulting in Hospitalization $\geq 24$ hrs	10 Calendar Days	24-Hour 5 Calendar Days
Not resulting in Hospitalization $\geq 24$ hrs	Not required	

**NOTE:** Protocol specific exceptions to expedited reporting of serious adverse events are found in the Specific Protocol Exceptions to Expedited Reporting (SPEER) portion of the CAEPR.

**Expedited AE reporting timelines are defined as:**

- “24-Hour; 5 Calendar Days” - The AE must initially be submitted electronically within 24 hours of learning of the AE, followed by a complete expedited report within 5 calendar days of the initial 24-hour report.
- “10 Calendar Days” - A complete expedited report on the AE must be submitted electronically within 10 calendar days of learning of the AE.

Serious adverse events that occur more than 30 days after the last administration of investigational agent/intervention and have an attribution of possible, probable, or definite require reporting as follows:

**Expedited 24-hour notification followed by complete report within 5 calendar days for:**

- All Grade 3, 4, and Grade 5 AEs

**Expedited 10 calendar day reports for:**

- Grade 2 AEs resulting in hospitalization or prolongation of hospitalization

For studies using PET or SPECT IND agents, the AE reporting period is limited to 10 radioactive half-lives, rounded UP to the nearest whole day, after the agent/intervention was last administered. Footnote “1” above

applies after this reporting period.

Effective Date: May 5, 2011

### 9.3.3 Other Reporting

Any Serious Adverse Event, as described in Section [9.3.1](#), including death due to any cause, which occurs during this study must be **reported immediately (within 24 hours)** to the ABTC Central Office.

A phone call must be made to:

#### Secondary Malignancy

A secondary malignancy is a cancer caused by treatment for a previous malignancy (e.g., treatment with investigational agent/intervention, radiation or chemotherapy). A secondary malignancy is not considered a metastasis of the initial neoplasm.

CTEP requires all secondary malignancies that occur following treatment with an agent under an NCI IND/IDE be reported via CTEP-AERS. Three options are available to describe the event:

- Leukemia secondary to oncology chemotherapy (e.g., acute myelocytic leukemia [AML])
- Myelodysplastic syndrome (MDS)
- Treatment-related secondary malignancy

Any malignancy possibly related to cancer treatment (including AML/MDS) should also be reported via the routine reporting mechanisms outlined in each protocol.

#### Second Malignancy:

A second malignancy is one unrelated to the treatment of a prior malignancy (and is NOT a metastasis from the initial malignancy). Second malignancies require ONLY routine reporting via CDUS unless otherwise specified.

#### Second Malignancy

A second malignancy is one unrelated to the treatment of a prior malignancy (and is NOT a metastasis from the initial malignancy). Second malignancies require ONLY routine reporting via CDUS unless otherwise specified.

#### **9.4 Routine Adverse Event and Data Reporting**

All Adverse Events **must** be reported in routine study data submissions. **AEs reported expeditiously through CTEP-AERS must also be reported in routine study data submissions.**

This study will be monitored by the Clinical Data Update System (CDUS). The ABTC Central Office is responsible for compiling and submitting CDUS data to CTEP for all participants and for providing the data to the principal investigator for review.

[figure not shown]
[figure not shown]
[figure not shown]
[figure not shown]
Cumulative CDUS data will be submitted quarterly to CTEP by electronic means. Reports are due January 31, April 30, July 31 and October 31.

## 9.5 Exploratory Correlative Studies

### 9.5.1 Immunohistochemical Detection of Topoisomerase II $\alpha$ and MPG on Archived Tumor Samples

Formalin fixed, paraffin embedded pretreatment tumor specimens will be stained with antibodies to methylpurine DNA-glycosylase (MPG) and topoisomerase II $\alpha$  (Topo II $\alpha$ ) in the IHC lab of the Tissue Resources Core of the Case Comprehensive Cancer Center, under the direction of [name]. The IHC Core has extensive experience in method development and validation of IHC for use as correlative markers in clinical trials. The relevant antibodies have been identified and methods developed for the targets.

IHC results will be determined by a combination of the percentage of tumor cell staining and the intensity of tumor cell staining. These results will be correlated between the responders and non-responders in the trial.

**Methyl Purine DNA-Glycosylase**  
(Abcam#ab55461)

**Topoisomerase II $\alpha$**   
(BioCare#API3045AA)

Figure 1: Immunohistochemical staining of clinical GBM specimens. Archived GBM specimens were identified, slides were cut, antigen retrieval was performed and slides stained with the indicated primary antibodies and HRP conjugated anti-mouse secondary antibodies and DAB detection performed in a Nemesia IHC Autostainer.

## Sample Packaging and Shipping

Archived tumor tissue from the initial resection at diagnosis of glioblastoma (pre-treatment) will be collected from patients when sufficient tissue is available. At the time of registration, prior to beginning treatment, a tumor tissue form indicating availability

will need to be completed and signed by a pathologist. This form provides written documentation of the availability of tissue for this study and the pathologist's agreement to send it as described below. A minimum of 10 unstained slides will be requested. The associated pathology report from the institution of collection should be shipped with the slides.

Ship slides and associated pathology report to:

[name]  
Scientific Director, Translational Research Core Facility  
Case Comprehensive Cancer Center  
[name]  
[name]  
[name]  
Office: [contact]  
Lab: [contact]  
Email: [[contact]](mailto:[contact])

## **10.0 OFF TREATMENT/OFF STUDY CRITERIA**

Each subject has the right to withdraw from the study at any time without prejudice. The investigator may discontinue any subject's participation for any reason, including adverse event or failure to comply with the protocol (as judged by the investigator such as compliance below 80%, failure to maintain appointments, etc.).

Should a subject withdraw from the study, the reason must be stated on the case report form, and a final evaluation of the subject should be performed.

Patients who go off treatment must be followed for adverse events (AEs) for at least 30 days from the last dose of TRC102.

### **10.1 Off Treatment Criteria**

1. Disease Progression: Remove patient from protocol therapy at the time progressive disease is documented. Disease progression is defined as: Progressive neurologic abnormalities not explained by causes unrelated to tumor progression (e.g. anticonvulsant or corticosteroid toxicity, electrolyte abnormalities, hyperglycemia, etc.) or a greater than 25% increase in the measurement of the tumor by MRI scan. If neurologic status deteriorates, on a stable or increasing dose of steroids, or if new lesions appear on serial MRI, further study treatment will be discontinued.
2. Adverse Event:
  - Intercurrent illness that prevents further administration of treatment
  - Patients who experience unacceptable toxicity. Patients removed from study for unacceptable adverse events will be followed until resolution or stabilization of

the adverse event.

3. Patient Withdrawal: Patient's refusal to continue treatment: in this event, document the reason for withdrawal.
4. Non Compliance: Failure to comply with protocol (as judged by the investigator such as compliance below 80%, failure to maintain appointments, etc.)
5. Physician Decision: If at any time the treating physician feels constraints of this protocol are detrimental to the patient's health remove the patient from protocol therapy.
6. Protocol Defined Delay:
  - Patients who experience a treatment-related toxicity causing a delay in treatment >21 days
  - Delay in protocol >28 days for major events or other non-treatment related delays
  - Patients who require >2 dose reductions
  - If either TRC102 or temozolomide is permanently discontinued, patient will be off treatment.
  - Patients who must be put on an enzyme-inducing anti-epileptic drug (EIAED) during the study
7. Death

## **10.2 Off Study Criteria**

Patients will only be off study at the time of death. All patients will be followed for survival every 2 months for the first two years from the off treatment date; after 2 years, patients will be followed every 6 months until death. Survival status may be obtained by phone call, clinic visit, or medical records (e.g. physician notes/laboratory results of clinic or hospital visit). Please note that additional survival status reports will be required twice yearly for ABTC Central Office reporting.

## 11.0 STATISTICAL CONSIDERATIONS

### Primary Objectives

#### Arm 1

Objective response

#### Arm 2

Objective response

### Secondary Objectives

1. Toxicity and safety of the combination TMZ and TRC102
2. Progression-free survival, progression-free survival at 6 months, and overall survival

### Exploratory Objective

Correlation of MPG, topo II $\alpha$ , and MGMT with response, PFS, and overall survival

### Sample size justification for primary endpoints:

Arm1: The Arm 1 study is to test the hypothesis that the combination treatment of TMZ and TRC102 will achieve 30% radiographic response rate (PR+CR) in patients with first recurrence of glioblastoma. A 2-stage design (minimax design) would discriminate between true response rates of no more than 13% and at least 30%. Maximum trial size would be set at 31 evaluable patients. If at least 7 responses (at least 22.5%) were observed among the 31 evaluable patients, this regimen would be considered worthy of further testing in this disease. If no more than 2 responses (no more than 10.5%) were observed among the initial 19 patients, the study would be terminated early and declared negative. This design yields at least 85% power to detect a true response rate of at least 30%. It yields at least .90 probability of a negative result if the true response rate is no more than 13%, with at least .54 probability of early negative stopping.

The Arm 2 study for bevacizumab-refractory patients is warranted only if the Arm 1 study meets its efficacy criteria. Arm 2 will not open without prior discussion between ABTC and CTEP.

Arm2: Arm 2 is a single arm study to test the hypothesis of clinical benefit of 30% radiographic response rate (PR+CR) for patients who had multiple numbers of prior therapies and are bevacizumab refractory, who are treated with TMZ and TRC102, and who continue bevacizumab. A safety run with 6 patients will be conducted prior to hypothesis testing in Arm 2. The expected DLT rate is  $\leq 33\%$ . If more than 2 patients experience dose limiting toxicity (DLT) associated with this regimen, Arm 2 will not be pursued further for safety reasons. If 2 or fewer patients experience DLT, Arm 2 will be

conducted using Simon's two-stage design. The 6 patients who were treated in the initial safe run will be counted as part of the first stage patients in the two-stage design.

Using Simon's two-stage design, if at least 7 responses (at least 20%) were observed among the 35 evaluable patients, this regimen could be considered worthy of further testing in this disease. If no more than 2 responses (no more than 11%) were observed among the initial 18 patients, the study would be terminated early and declared negative. This design yields at least 90% power to detect a true response rate of at least 30% from a null of 10% at an alpha level of 0.05 (one-sided). It yields 73% probability of early stopping if the true response rate is 10%.

All secondary and exploratory objective outcomes will be analyzed using standard descriptive statistical methods. Potential statistical comparisons are considered exploratory.

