## 2.0 BACKGROUND AND RATIONALE

### 2.1 Glioblastoma

Although the recent addition of temozolomide (TMZ) to radiation therapy for the treatment of glioblastoma (GBM) has resulted in improved outcomes, the estimated 2-year survival with maximal therapy remains only 27% (Stupp 2005, Stupp 2009). Almost all GBMs progress, with a median time to progression of approximately 7 months. The prognosis is very poor for patients who have progressive/recurrent GBM. There is currently no standard therapy for recurrence. Salvage chemotherapies are largely ineffective, with progression-free survival at 6 months (PFS6) rates of 10-15%. Bevacizumab therapy at recurrence is associated with a high response rate, but not significantly increased survival. Survival after failure of bevacizumab administered for GBM recurrence is very poor with a median survival of 4-6 months and PFS 6 of 0 (Reardon 2012). Hence, new therapies for recurrent GBM are urgently needed.

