### **3.0 PATIENT ELIGIBILITY CRITERIA**

#### **3.1 Patient Sample**

Sample Size:

Arm 1: 31 bevacizumab-naïve patients

Arm 2: 35 bevacizumab-refractory patients

Accrual Rate:

4-5 patients per month

Gender:

Male and female

Age:

Patients must be at least 18 years of age.

Race:

Minorities will be actively recruited. No exclusion to this study will be based on race or ethnicity.

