#### Arm 2: bevacizumab-refractory patients

*(This arm will only activate if Arm 1 meets the statistical criteria of efficacy as defined in Section [11.0](#))*

Arm 2 will estimate the efficacy of TRC102 and TMZ, as measured by response rate, in bevacizumab-refractory glioblastoma (patients must have progressed/recurred following prior treatment with bevacizumab but should continue receiving bevacizumab as clinically indicated).

All patients will receive the maximum tolerated dose of oral TRC102 as determined in the NCI phase I trial, 150mg flat dose, combined with temozolomide 150mg/m^2 on days 1-5 every 28 days. The dose of temozolomide will remain at 150 mg/m^2 throughout the study.

TRC102 and TMZ are being given together as a combined treatment. If for any reason a patient is permanently taken off TRC102 or TMZ the patient will be off treatment.

An MRI will be performed prior to every odd-numbered cycle (every 8 weeks).

Patients will continue receiving TRC102 and TMZ until they meet the criteria for disease progression or other criteria for going off treatment (Section [10.0](#)). All patients will be followed for survival.

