## **8.2 Assessment of Response**

Assessment of response will begin with the MRI performed just prior to *every odd-numbered* treatment cycle. If during any scheduled MRI, the subject has a Complete Response or Partial Response, the MRI should be repeated prior to the next cycle. All scans are to be compared to the smallest measurement scan to date. The subject will then return to the every odd-numbered cycle schedule. This is required to confirm the duration of response. Subjects will be classified as responders if they have a minimum duration of response for 4 weeks at any time after the first cycle of TRC102. MRI scans of subjects showing tumor response will be centrally reviewed by a neuroradiologist who will independently assess tumor size and compute percent tumor regression.

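### Must Section 11.0 fix a date for the stage-1 response count and say whether accrual waits for it?

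*Combined protocol and SAP*

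**What the plan says.** Section 11.0 (sample size justification) sets a two-stage design for each arm. Arm 1 has 19 patients in stage 1 and 31 in all, and at least 7 responses count as success. Its futility rule reads: "If no more than 2 responses (no more than 10.5%) were observed among the initial 19 patients, the study would be terminated early". The plan describes this design as one "with at least .54 probability of early negative stopping" when the true rate is no more than 13%. Arm 2 has 18 then 35 patients, again with success at 7 or more: "If no more than 2 responses (no more than 11%) were observed among the initial 18 patients, the study would be terminated early". The stated chance of stopping early there is 73% at a 10% rate.

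The timing inputs lie elsewhere. Section 3.1 plans "4-5 patients per month", and Section 4.0 runs the arms one after the other. Section 4.1 sets the imaging: "An MRI will be performed prior to every odd-numbered cycle (every 8 weeks". Section 8.1 requires a response to be confirmed by a scan 4 weeks later. Section 8.2 classes subjects as responders "if they have a minimum duration of response for 4 weeks at any time after the first cycle of TRC102", with no closing date. Section 7.0 has sites check protocol status and slot availability on the consortium's website before raising the study with a patient.

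**The concern.** A futility rule protects patients only if its result arrives before the remaining places are filled. Here the first scan comes 8 weeks after treatment starts and confirmation takes 4 weeks more, while accrual is fast relative to a second stage of 12 patients. Section 11.0 gives neither a count date nor an instruction to hold registration. Read literally, an arm could be declared negative on its first 19 patients after most of the other 12 had been enrolled.

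The missing date is a second worry. Section 8.2 lets a response emerge at any time after cycle 1. An open-label team holding 2 responses of 19 could therefore stop, or wait for a third, and either would fit the text. At stake are the number of patients given an inactive regimen and, at the boundary, some discretion over whether the arm continues.

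**Working it through.** **Inputs.** Designs and rates are from Section 11.0, accrual of 4-5 per month from Section 3.1, the 8-week scan from Section 4.1 and the 4-week confirmation from Section 8.1. One month is 30.44 days. Assumptions: even accrual, all patients evaluable, no delay between registration, treatment start and scan reading.

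**1. The plan's own figures reproduce.** With X1 the stage-1 responses:

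- Arm 1 at 13%: P(X1 ≤ 2 of 19) = 0.0709 + 0.2014 + 0.2708 = 0.543. Requiring X1 ≥ 3 and a total of at least 7 of 31 gives a false-positive probability of 0.095 at 13% and power of 0.854 at 30%. The plan states at least .54, at least .90 negative, and at least 85%.
- Arm 2 at 10%: P(X1 ≤ 2 of 18) = 0.1501 + 0.3002 + 0.2835 = 0.734. The false-positive probability is 0.047 and power is 0.902. The plan states 73%, 0.05 and 90%.

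These values depend only on the responses among the first 19 (or 18) and all 31 (or 35) patients. Enrolling patient 20 before the count is known alters none of them, provided the rule is still applied to the first 19.

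**2. Overrun if accrual is not held.** Entries = rate × waiting time.

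- 8 weeks: 4 × 56/30.44 = 7.4; 5 × 56/30.44 = 9.2.
- 12 weeks: 4 × 84/30.44 = 11.0; 5 × 84/30.44 = 13.8, which exceeds Arm 1's 12 places. This wait arises only when an unconfirmed response decides the boundary.

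**3. Expected enrolment under the null rate.** With a hold, E[N] = n1 + (1 − early stop) × (n − n1). Without one, add early stop × entries.

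| | Hold | No hold, 4/month | No hold, 5/month |
|---|---|---|---|
| Arm 1, 13% | 19 + 0.457 × 12 = 24.5 | 24.48 + 0.543 × 7.36 = 28.5 | 24.48 + 0.543 × 9.20 = 29.5 |
| Arm 2, 10% | 18 + 0.266 × 17 = 22.5 | 22.53 + 0.734 × 7.36 = 27.9 | 22.53 + 0.734 × 9.20 = 29.3 |

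In Arm 1 the difference is 4.0-5.0 patients, or 61-77% of the expected saving of 0.543 × 12 = 6.5. The Arm 2 row applies only if Arm 2 opens and passes its 6-patient safety run. That run ends the arm if more than 2 patients have a DLT. At a 33% DLT rate, P(more than 2 of 6) = 0.31.

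**4. How much the open response window matters.** The documents give no share of late responses, so take 10-20% first seen at the second scan (week 16) as an assumption. At patient 19's week-8 scan, 8 of the 19 patients (4/month) or 10 (5/month) have not had a week-16 scan. Expected late responders at 13% run from 8 × 0.13 × 0.10 = 0.10 to 10 × 0.13 × 0.20 = 0.26.

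**5. What fixing an early date would cost.** Suppose stage 1 counts only responses first seen by that week-8 date, with later ones added to the final total. Power at 30% becomes:

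| Late share | Arm 1 (from 85.4%) | Arm 2 (from 90.2%) |
|---|---|---|
| 10% | 84.6-84.8% | 88.6-88.9% |
| 20% | 83.4-83.9% | 86.5-87.4% |

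A hold also delays good trials. Take the pause as max(0, 84 days − (n1 − index of the third responder) × days between entries), at a true 30% rate. Its mean in trials that continue is 18-26 days in Arm 1 and 21-31 days in Arm 2.

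**The case for a change.** The strongest argument for a change is that the futility stop is the only interim efficacy safeguard in Section 11.0 and that a few sentences would secure it. Without them nothing obliges the team to hold accrual, and a team at 2 of 19 can choose when to count. If an assumed exponential curve is fitted to the 10-15% six-month progression-free rate in Section 2.1, then 4.5-6.4 of the 19 patients are still progression-free at patient 19's week-8 scan. At least 2.5-4.4 of them would be non-responders whose status could still change.

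Part of this stands. The text is silent, and at exactly 2 responses the team has discretion. The rest is weaker than it looks. Being progression-free is not the same as being likely to respond: with a late share of 10-20%, the expected number of late responders is 0.1-0.3. The window is also not endless in practice, because treatment stops at progression and Section 10.2 then asks only for survival follow-up (Section 10.0 adds 30 days of adverse-event follow-up). Nor is there a contradiction, since no section says accrual runs on without interruption. Holding registration while stage 1 matures is an ordinary way to run a two-stage design, and the central slot check gives the coordinating office the means.

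**Conclusion.** The concern does not call for a change. Section 11.0 leaves out an operational detail that a trial team can fill sensibly, and no single way of filling it is clearly better. Holding accrual with an early count saves patients but, under the late-response assumption, takes power slightly below the stated 85% and 90%. A later count protects power at the price of a longer pause. Not holding costs 4-5 expected patients in Arm 1 at a 13% rate (28.5-29.5 against 24.5) and leaves false-positive rate, power and the .54 and 73% stopping probabilities as stated. Each is defensible.

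The 7-9 early entrants arise only if accrual is not held, which the plan neither says nor implies. The figures rest on even accrual at the planned rate, all patients evaluable, and no lag in scan reading. The power costs also rest on an assumed late-response share. The Arm 2 figures are conditional on Arm 1 meeting its efficacy criteria, the discussion between the consortium and CTEP, and the safety run.
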